3.2 Subject disposition, protocol deviations, demographics and other baseline characteristics

The FAS will be used for all baseline and demographic summaries and listings.

3.2.1 Subject disposition

FAS will be used for the patient disposition summary tables and listings. The following information will be summarized.

1. Number (%) of patients who are still on-treatment (based on the absence of the 'End of Treatment' page);
2. Number (%) of patients who discontinued the study treatment (based on the 'End of Treatment' page)
3. Reasons for study treatment discontinuation (based on 'End of Treatment' page).

3.2.2 Protocol deviations

The number and percentage of patients in the FAS with any protocol deviation will be tabulated by the deviation category (as specified in the data handling plan) and by treatment group and overall.

Protocol deviations will also be listed by center.

3.2.3 Protocol eligibility criteria

Protocol eligibility criteria will be provided as follows:

1. A list of screen failures along with their failed inclusion/exclusion criteria,
2. A list of informed consent signature dates,
3. A list of enrolled patients but not-treated along with the primary reason for not continuing into the study. The reason for not continuing in the study will be obtained from the end of treatment page. Additional details, if included in the comments domain or in the end of study CRF page, will be included.
4. Patients' eligibility to analysis sets defined in [section 2.2](#) and their allocation to treatment.

3.2.4 Analysis sets

The number and percentage of patients in each analysis set (definitions are provided in [section 2.2](#)) will be summarized by treatment groups. Patients' eligibility to analysis sets will also be listed.

3.2.5 Demographics

The following demographic variables will be summarized by study phase following the general presentation specified in [section 3.1](#):

Continuous variables:

- Age (years)
- BMI (kg/m²)

Categorical variables:

- gender (male/ female)
- race (Caucasian/Black/ Asian/ Native American/ Pacific Islander/unknown/other)
- ECOG performance status at screening (0/ 1/ 2)

3.2.6 Other baseline characteristics

The following baseline characteristics will be summarized:

International Prognostic Scoring System (IPSS) Risk factors at the time of diagnosis, MF classification, prior PRBC transfusion status, and JAK2V617F status, bone marrow fibrosis grade (most recent result prior to study entry).

3.2.7 Medical history / current medical conditions

Medical history and ongoing conditions will be summarized and listed by the redefined study treatment groups (details can be found in RAP M7.1 section 1.2.1). Separate summaries will be presented for ongoing and historical medical conditions. The summaries will be presented by primary system organ class and preferred term. Medical history/current medical conditions are coded using the medical dictionary for regulatory activities (MedDRA) terminology.

3.2.8 Prior Anti-neoplastic therapy

Prior anti-cancer therapy will be listed in three separate listings: myeloproliferative Neoplasm Directed Therapy – Medication, anti-neoplastic radiotherapy and surgery.

The number and percentage of patients recording any prior anti-neoplastic medications (myeloproliferative neoplasm directed therapy-medication), prior anti-cancer radiotherapy and prior anti-cancer surgery will be summarized.

Prior anti-neoplastic medications will be classified and summarized by therapy type (chemotherapy, hormonal therapy, immunotherapy, targeted therapy, and other), ATC class (if appropriate), preferred term and treatment.

Any indication-specific significant prior anti-neoplastic medications will be identified in the summaries mentioned above.

Anti-neoplastic therapies since discontinuation of study drug will be listed and summarized by ATC class, preferred term and treatment and overall by means of frequency counts and percentages in separate summaries.

Partial dates will be imputed according to the algorithm specified in [section 2.1.11.4](#).

3.3 Study drug

Summaries of study drug administration characteristics will be provided for both LDE225 and INC424 separately as indicated: duration of exposure to study drug; exposure to study drug measured by cumulative dose, average daily dose, actual dose intensity (DI), and relative dose intensity (RDI); and dose reductions and interruptions, which are defined in the following sections.

Listings of study drug administration records for LDE225 and INC424, as recorded in CRFs, along with dose reductions and dose interruptions will be provided.

The safety set will be used for all summaries and listings of study treatment.

3.3.1 Duration of exposure

The number and percentage of patients treated with each study treatment will be summarized by study phase. The following formula will be used to calculate duration of study drug exposure for patients who took at least one dose of any of the components of the study treatment. Duration of exposure includes the periods of temporary interruption of study drug for any reason.

For patients *who discontinued permanently* from the study as of the data cut-off date:

Duration of exposure (days) = last dosing date of any study treatment component – first dosing date of any study treatment component + 1

For patients *who are still on-treatment* as of data cut-off date:

Duration of exposure (days) = data cut-off date – (first dosing date of any study treatment component) + 1.

Date of first administration of study treatment and date of last administration of study treatment are defined in [section 2.1.3](#) and [section 2.1.4](#).

In addition, duration of exposure will be categorized in intervals defined in RAP M7. The number and percentage of patients with duration of exposure per category will be summarized. Cumulative duration of exposure will also be summarized. For patients who did not take any study treatment the duration of exposure is defined as zero. The following categories for exposure to study treatment will be analyzed:

- < 2 weeks
- \geq 2 weeks to < 4 weeks
- \geq 4 weeks to < 8 weeks
- \geq 8 weeks to < 12 weeks
- \geq 12 weeks to < 24 weeks
- \geq 24 weeks to < 48 weeks
- \geq 48 weeks to < 106 weeks
- \geq 106 weeks

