6.3.1.1 Optional dose tapering strategy for INC424 in the event of discontinuation

When INC424 therapy is stopped, return of constitutional symptoms associated with elevated cytokines (e.g. night sweats, fever, fatigue) that had been suppressed while on therapy is expected. When a decision is made to permanently discontinue INC424 therapy for reasons other than for hematologic safety, a dose tapering strategy may be considered, based on evaluation of the condition of the patient, current dosing regimen and the clinical judgment of the Investigator, so that symptoms may return to pre-treatment condition more slowly. If considered to be medically necessary, the Investigator may use any treatment to manage withdrawal from INC424 including a gradual tapering of the study drug dosage or use of other medications to manage events occurring after discontinuation. Short-term courses of corticosteroids at doses > 10 mg/day have been used in patients with MF and may be considered as part of a tapering strategy. Corticosteroids may be started prior to, or concurrent with, INC424 tapering. When a decision has been made to discontinue the patient with utilization of a tapering strategy, regardless of the use of concomitant medications, safety data will continue to be assessed in accordance with the protocol for a period of time as least through the continued administration on INC424 and 30 days after for AEs.

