2.1.4 Date of last administration of study treatment

The date of last administration of study drug is defined as the last date when a nonzero dose of study drug was administered and recorded on LDE225 or INC424 DAR eCRF. This date of last administration of study treatment will also be referred as the *last date of study treatment*.

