3.3.2 Cumulative dose

Cumulative dose (mg) is defined as the total dose given during the study treatment exposure and will be summarized by study phase, treatment components separately.

For patients who did not take any drug the cumulative dose is by definition equal to zero.

Cumulative dose will be calculated from the dose administration pages of LDE225 and INC424.

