3.3.4 Actual dose intensity and relative dose intensity

Dose intensity (DI) [mg/day], planned dose intensity (PDI) [mg/day], and relative dose intensity (RDI) [%] will be summarized by study phase, overall (while on-treatment).

Frequencies for RDI will also be categorized in intervals for LDE225 and INC424 as follows: <70%, ≥70% - ≤90% and > 90%. The number and proportion of patients within each category will be presented.

Actual DI for patients with non-zero duration of exposure is defined as follows:

$$\text{DI (mg/day)} = \text{Cumulative dose (mg)} / (\text{Duration of exposure (days)})$$

For patients who did not take any drug, DI will be zero.

Planned dose intensity (PDI) for patients with non-zero duration of exposure is defined as following:

$$\text{PDI (mg/day)} = \text{Cumulative planned dose (mg)} / (\text{Duration of exposure (days)})$$

The calculation of planned dose is based on the initial assigned dose regardless the dose interruption. Cumulative planned dose is the per-protocol planned dose cumulated over the actual duration on study treatment. For patients who did not take any drug the PDI is by definition equal to zero mg/day.

Relative dose intensity (RDI) is defined as following:

$$\text{RDI (\%)} = \text{DI (mg/day)} / \text{PDI (mg/day)} * 100$$

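### SAP 3.3.1 defines exposure duration only for the combination, although SAP 3.3 promises it per drug; when the two last dose dates differ, the drug stopped first gets too long a duration and too low a dose intensity (minor, descriptive tables only)

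*SAP*

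**What the plan says.** SAP 3.3 opens with this commitment: "Summaries of study drug administration characteristics will be provided for both LDE225 and INC424 separately as indicated: duration of exposure to study drug". The same list covers cumulative dose, DI and RDI. Protocol 10.3.1 likewise speaks of the duration of LDE225 and INC424 treatment.

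SAP 3.3.1 then gives one formula. For patients who have discontinued, duration runs from the "first dosing date of any study treatment component" to the "last dosing date of any study treatment component", plus one day. For patients still on treatment, the end date is the data cut-off. SAP 2.1.4 is consistent with this: the last date of study treatment is "the last date when a nonzero dose of study drug was administered and recorded on LDE225 or INC424 DAR eCRF".

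The quantities built on this duration are:
- Cumulative dose (SAP 3.3.2) is drug-specific: it "will be summarized by study phase, treatment components separately".
- DI (SAP 3.3.4) is cumulative dose divided by the SAP 3.3.1 duration.
- Planned dose intensity (PDI) uses the same denominator, and "Cumulative planned dose is the per-protocol planned dose cumulated over the actual duration on study treatment", based on the initially assigned dose whether or not dosing was interrupted.
- RDI is DI/PDI, tabulated for each drug as below 70%, 70–90% and above 90%.

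Protocol 6.3.1.1 allows the investigator to manage INC424 withdrawal with, among other options, "a gradual tapering of the study drug dosage". It gives no taper length.

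**The concern.** Applied literally, the formula gives both drugs the same duration in every patient, so the per-drug duration summary carries no per-drug information. The mismatch then enters dose intensity, because a drug-specific numerator is divided by a combination-level denominator. Once one drug has been taken for the last time, its planned dose keeps accruing until the other drug's last dose, or until the cut-off in patients still on treatment. Those days count as exposure to a drug that is no longer taken.

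The loss is also hard to trace in the output. SAP 3.3.5 does not count the last zero dose before permanent discontinuation as an interruption. Trailing drug-free days would therefore lower RDI without appearing in the interruption table. A reader of the CSR could take an RDI of 75% as evidence of poor tolerability in a patient who took every planned dose of that drug.

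**Working it through.** The documents state no exposure or dose-intensity figure, so there is nothing to reproduce. The check applies the SAP formulas to a simple patient.

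**Inputs**
- Drug dose: 400 mg LDE225 once daily, the dose in the confirmed RPIID (Protocol, Amendment 2 rationale). It cancels out of RDI.
- L: days of that drug at full dose. Illustrative values: 42, 84, 168, 336.
- T: further days on which only the partner drug is taken. The documents give no value; 7 to 28 days is assumed.

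**Formulas under SAP 3.3.1 and 3.3.4**
- Duration = L + T
- DI = 400 × L/(L + T)
- PDI = 400 × (L + T)/(L + T) = 400
- RDI = DI/PDI = L/(L + T)

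With the drug's own first and last dose dates, duration = L, DI = 400 mg/day and RDI = 100% for any T.

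**Example.** L = 84, T = 14: duration 98 days instead of 84; DI = 400 × 84/98 = 342.9 mg/day instead of 400; RDI = 84/98 = 85.7% instead of 100%.

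**RDI under the SAP formula (true value 100%)**

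| L (days) | T=7 | T=14 | T=21 | T=28 |
|---|---|---|---|---|
| 42 | 85.7% | 75.0% | 66.7% | 60.0% |
| 84 | 92.3% | 85.7% | 80.0% | 75.0% |
| 168 | 96.0% | 92.3% | 88.9% | 85.7% |
| 336 | 98.0% | 96.0% | 94.1% | 92.3% |

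**Category shifts.** A fully dosed patient leaves the >90% class when L/(L+T) ≤ 0.9, that is T ≥ L/9: from 5, 10, 19 and 38 days for the four values of L. The patient falls below 70% when T > 3L/7: from 19, 37, 73 and 145 days. With T = 0 there is no effect.

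**Symmetry.** Nothing in the formula is specific to LDE225. If LDE225 is the last drug taken, INC424 has the overstated duration and the lowered RDI.

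**A test of the obvious repair.** Suppose LDE225 is taken in full for 84 days and then held for toxicity. INC424 continues for 21 days (assumed), and both drugs are then stopped.
- SAP rule: RDI = 84/(84+21) = 84/105 = 80%.
- Ending the clock at the last non-zero LDE225 dose: RDI = 84/84 = 100%, so the hold disappears.

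Now add a 14-day INC424 taper after the decision to stop.
- SAP rule: 84/119 = 70.6%.
- Counting the hold but not the taper: 84/105 = 80%.

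The two kinds of trailing days therefore need different treatment.

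**The case against.** The best defence is that a common duration was intended. SAP 2.1.1 defines study treatment as the combination. SAP 3.3.1 speaks of exposure to study treatment, whereas SAP 3.3.2 adds that components are handled separately. SAP 3.3 qualifies its promise with 'as indicated', and details are referred to a RAP M7 document that is not available here. This explains how the formula may have arisen, but it does not supply a per-drug duration, and SAP 3.3 names duration among the per-drug summaries. A reader might infer that the per-drug table cannot be produced at all. That goes too far, because dosing is recorded and listed by drug; only the definition is missing.

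The trigger is also narrow, and this part of the objection stands. Protocol 4.3.1 requires the partner drug to be discontinued when either drug is. The taper in Protocol 6.3.1.1 is optional and limited to discontinuations for reasons other than hematologic safety. That LDE225 has already stopped when the taper begins is a plausible reading, not an express statement.

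A reader might also infer a common or large distortion from the fact that 14 of 50 treated patients had discontinued by 06 February 2015. The documents do not support that. Those discontinuations had several causes, and no count of tapers is given. Longer exposure also dilutes the effect: at 336 days with a 14- or 28-day gap, RDI stays above 90%.

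Finally, for a terminal toxicity hold the SAP rule is more informative than one that stops at the last non-zero dose. This is correct, and it shapes the fix.

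**Conclusion.** The inconsistency is real and its direction is certain: whenever the two drugs' last dose dates differ, the drug stopped first has its duration overstated by T days. If the trailing days are taper days, its RDI is understated by the factor L/(L+T). The size in this trial is unknown, because both T and its frequency are assumptions. The table above is an illustration for fully dosed patients, not an estimate.

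The stronger reading, that LDE225 tolerability is systematically misreported, is not supported. The error can fall on either drug, it vanishes when the dates coincide, and in the case of a terminal hold the lower RDI is the honest figure.

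The issue is minor. It is confined to the descriptive duration, DI and RDI tables. Average daily dose (SAP 3.3.3) counts dosing days only and is unaffected. Cumulative dose, the dose-determining set (which uses missed-dose counts), the interim rule and the primary analyses do not use this duration.

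**What to change.** Amend SAP 3.3.1 and 3.3.4 as follows.

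1. Keep the any-component duration, labelled as overall study-treatment exposure.
2. Define each drug's duration from its own first to its own last non-zero dose.
3. Compute each drug's DI, PDI and RDI over that drug's own treatment period. Exclude days on which only the partner drug is being tapered after the decision to discontinue. Keep counting as planned dose any terminal hold of the drug up to that decision. State that this period can be longer than the duration in item 2.
4. State which recorded date marks the decision. SAP 2.1.8 refers to a discontinuation date on the End of Treatment page; whether it captures the decision or the last dose should be confirmed before it is used.
5. For patients still on treatment at the cut-off, say how a drug already stopped or on hold is handled.

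The cost is a few lines of definition and the matching programming. Dosing is already recorded by drug, so no new dosing data are needed. The only open item is the decision date in item 4.

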3.3.2 Cumulative dose

Cumulative dose (mg) is defined as the total dose given during the study treatment exposure and will be summarized by study phase, treatment components separately.

For patients who did not take any drug the cumulative dose is by definition equal to zero.

Cumulative dose will be calculated from the dose administration pages of LDE225 and INC424.

3.3.3 Average daily dose

Average daily dose is defined as follows:

Average daily dose (mg/day) = cumulative dose / number of dosing days.

Drug free day(s) are not counted in the number of dosing days.

3.3.4 Actual dose intensity and relative dose intensity

Dose intensity (DI) [mg/day], planned dose intensity (PDI) [mg/day], and relative dose intensity (RDI) [%] will be summarized by study phase, overall (while on-treatment).

Frequencies for RDI will also be categorized in intervals for LDE225 and INC424 as follows: <70%, ≥70% - ≤90% and > 90%. The number and proportion of patients within each category will be presented.

Actual DI for patients with non-zero duration of exposure is defined as follows:

$$\text{DI (mg/day)} = \text{Cumulative dose (mg)} / (\text{Duration of exposure (days)})$$

For patients who did not take any drug, DI will be zero.

Planned dose intensity (PDI) for patients with non-zero duration of exposure is defined as following:

$$\text{PDI (mg/day)} = \text{Cumulative planned dose (mg)} / (\text{Duration of exposure (days)})$$

The calculation of planned dose is based on the initial assigned dose regardless the dose interruption. Cumulative planned dose is the per-protocol planned dose cumulated over the actual duration on study treatment. For patients who did not take any drug the PDI is by definition equal to zero mg/day.

Relative dose intensity (RDI) is defined as following:

$$\text{RDI (\%)} = \text{DI (mg/day)} / \text{PDI (mg/day)} * 100$$

3.3.5 Dose reduced, dose interrupted and dose discontinued permanently

Reduction: A reduction is defined as a decrease in dose from the protocol planned starting dose or a decrease from the previous non-zero dose for either INC424 or LDE225, even if this decrease has been directly preceded by an interruption. For example, in the sequence 20mg – 0mg – 10mg, the 10mg dose will be counted as a reduction.

Interruption: An interruption is defined as a zero dose on one or more days between two non-zero doses, for either INC424 or LDE225.

If, due to a dosing error, a patient receives higher than protocol planned starting dose and moves down to the planned starting dose then this is not be counted as a reduction, however if they move directly from a higher than planned starting dose down to a lower than protocol planned starting dose, then this is counted as a reduction.

Note: The last zero dose of INC424 and LDE225 (followed by permanent discontinuation) is not considered as a dose interruption. Additionally, two consecutive zero doses of INC424 (e.g. in the sequence 20 mg daily, 0 mg, 0 mg, 10 mg daily) will be counted as one interruption if the reasons for these two consecutive dose interruption are the same.

The numbers and percentage of patients who have the dose reduction, dose interruption or dose permanent discontinuation will be summarized by redefined study treatment group. For patients who had dose reductions/interruptions, counts of reductions or interruptions,

reductions only and interruptions only will be categorized and presented as specified in RAP M7.1.

3.4 Concomitant therapy

The FAS will be used for all concomitant medication tables and listings.

Concomitant therapy is defined as all interventions (therapeutic treatments and procedures) besides the study treatment that were administered to a subject preceding or coinciding with the study assessment period.

Concomitant medications entered into the database will be coded using the WHO Drug Reference List to allow for categorization by preferred term and using MedDRA for the procedures. In addition to categorizing medication data by preferred term, drugs are classified according to their ATC classification in order to present and compare how they are being utilized.

Concomitant medications and significant non-drug therapies taken concurrently with the study drug(s) will be listed and summarized by ATC class, preferred term and treatment arm by means of frequency counts and percentages. These summaries will include medications starting on or after the start of study treatment or medications starting prior to the start of study treatment and continuing after the start of study treatment.

Any prior concomitant medications or significant non-drug therapies starting and ending prior to the start of study treatment will be listed.

3.5 Primary analysis and primary variables

3.5.1 Phase Ib

3.5.1.1 Primary variable in phase Ib

The primary variable is the incidence of dose limiting toxicities (DLTs) in the first 6 weeks of treatment associated with continuous daily administration of LDE225 in combination of INC424. Estimation of the MTD of the combination treatment will be based upon the estimation of the probability of DLT in 6 weeks for patients in the dose-determining set using BLRM and guided by EWOC. This probability is estimated by the model in [section 3.5.1.2](#).

3.5.1.2 Statistical model, and method of analysis

Statistical model:

The model is formulated in the following way: let $\pi_1(d_1)$ be the probability of a DLT if INC424 is given as a single agent as dose d_1 , and let $\pi_2(d_2)$ the probability of a DLT if LDE225 is given as a single agent at dose d_2 , further let $\pi_{12}(d_1, d_2)$ be the probability of a DLT when LDE225 and INC424 are given in combination at doses d_1 and d_2 respectively. The dose-DLT relationship is then modeled as:

For a single-agent INC424:

$$\text{logit}(\pi_1(d_1)) = \log(\alpha_1) + \beta_1 \log\left(\frac{d_1}{d_1^*}\right) + \gamma I(\text{PLT} \leq 200 \times 10^9/\text{L})$$

For a single-agent LDE225:

$$\text{logit}(\pi_2(d_2)) = \log(\alpha_2) + \beta_2 \log\left(\frac{d_2}{d_2^*}\right)$$

For the combination of LDE225 and INC424:

$$\begin{aligned} \text{Odds}(\pi_{12}(d_1, d_2)) &= \frac{\pi_{12}(d_1, d_2)}{1 - \pi_{12}(d_1, d_2)} \\ &= \exp\left(\eta \frac{d_1 d_2}{d_1^* d_2^*} \frac{(\pi_1(d_1) + \pi_2(d_2) - \pi_1(d_1)\pi_2(d_2))}{(1 - \pi_1(d_1))(1 - \pi_2(d_2))}\right) \end{aligned}$$

Where I is the indicator function, $\text{logit}(\pi(d)) = \log[\pi(d)/\{1 - \pi(d)\}]$, $d_1^* = 30$ mg total daily dose (15 mg bid) and $d_2^* = 700$ mg (qd) are the reference doses of INC424 and LDE225 respectively, $\alpha_1, \alpha_2, \beta_1, \beta_2, \eta$ and $\gamma > 0$ are model parameters.

The parameter γ is related to the binary baseline covariate that indicates whether a patient's platelet count at baseline is $\leq 200 \times 10^9/\text{L}$ or not, and η is an interaction term between the two drugs.

Prior Specification:

The priors used in this study are in [Table 3-1](#). The further details on prior derivations and simulated operation characteristics can be found in the study protocol (Section 14.7, Appendix 7).

Table 3-1 Prior parameters obtained for CLDE225X2116

Parameter	Means	Standard deviations	Correlation
INC424 $\log(\alpha_1), \log(\beta_1)$	(-2.141, -0.180)	0.602, 0.634	0.085
LDE225 $\log(\alpha_2), \log(\beta_2)$	(-2.291, 0.721)	0.894, 0.773	-0.117
η (normal)	0.250	2.028	n/a
γ (log-normal)	-1.426	1.61	n/a

Dose recommendation

Dose recommendation will be based on summaries of the posterior distribution of model parameters and the posterior distribution of DLT rates, including the mean, median, standard

deviation, 95%-credibility interval, and the probability that the true DLT rate for each dose combination lies in one of the following categories:

- [0%, 16%) under dosing
- [16%, 35%) targeted toxicity
- [35%, 100] excessive toxicity

Following the principle of EWOC, after each cohort of patients the recommended dose combination is the one with the highest posterior probability of DLT in the target interval [16%, 35%) among the doses fulfilling the overdose-control criterion that there is less than 25% (posterior probability) chance of excessive toxicity. In addition, the maximum inter-cohort dose escalation is limited to 100% (i.e. up to 100% and 0% increase for LDE225 and INC424 respectively or 0% and up to 100% increase for LDE225 and INC424 respectively). The proposed combination meets the EWOC criteria (i.e. less than 25% chance that the true rate of DLTs lies within the interval [35% - 100%]). A clinical synthesis of the available toxicity information (including AEs that are not DLTs), PK, PD, and efficacy information as well as the recommendations from the BLRM will be used to determine the dose combination for the next cohort at a dose escalation teleconference.

Safety Expansion

After declaration of MTD and/or RPIID, the dose will be expanded by an additional 6 patients in order to further assess tolerability, safety and early efficacy. If two MTDs/RPIIDs are established, each MTD/RPIID will enroll an additional 6 patients in the safety expansion.

Listing of DLTs

DLTs will be listed and their incidence summarized by primary system organ class, worst grade based on the CTCAE version 4.03, type of adverse event by treatment. The dose-determining set will be used for these summaries.

